4.4.3 Planned Analyses

Statistical analyses will utilize an ITT approach and mixed models, one of two gold standards (together with multiple imputation) for handling missing outcome data in longitudinal studies.

For Primary Aim 1, we will examine condition effects on total drinks consumed over Weeks 2-10 (summarized over 4-week periods), controlling for baseline drinks. For this analysis, we will use mixed effects models with condition and sex as between-subject factors and time as a within-subject factor. We will also use the same modeling approach for secondary alcohol outcomes: drinks per drinking day, % heavy drinking, abstinent days (summarized in 4-week periods), and alcohol-related consequences, controlling for baseline, and will focus on effect size estimation rather than statistical testing. Using all repeated measures on individuals in the context of a mixed model will allow us to assess temporal patterns of change over time and to use all available data on individuals. Thus, this approach helps to avoid imputation of missing data and allows us to obtain unbiased and efficient estimates of the main and interactive effects. Mixed models will account for the correlation in alcohol outcomes measured in the same individual. We will use the Schwartz-Bayesian Information Criterion to elect the best-fitting variance-covariance structure. We will consider time as a categorical factor but will also test whether alcohol outcomes change linearly by condition over time. If an alcohol outcome is not normally distributed, we have several options including transforming data, utilizing alternative methods (e.g., generalized linear mixed models, nonparametric tests, Poisson and negative binomial generalized linear mixed models for count data). Hypothesis: The feedback group will report fewer total drinks than the assessment group.

For Secondary Aims 2.1-2.2, we will examine condition effects on PROMIS™ sleep quality and sleep-related impairment self-ratings, controlling for baseline, using mixed effects models. We will also analyze OURATM sleep, HRV, and RHR data (summarized over 2-week periods) using mixed effects models. We will transform or utilize alternative methods for non-normally distributed outcomes. We will also characterize the daily variations in OURATM sleep, HRV, RHR data and potential dynamic relationships between them and daily diary drinking data using methods for longitudinally intensive data (e.g., time-varying effects models). Hypothesis: The feedback group will report better sleep/health than the assessment group.

For Secondary Aim 2.3, we will summarize interview themes. We will also summarize use metrics and ratings for feedback and/or monitoring using descriptive statistics. We expect higher scores in the feedback group.

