4.1 Study Procedures

The goal of this study is to determine the feasibility and preliminary efficacy of this intervention for reducing drinking among heavy-drinking young adults, which if promising will lead to a larger trial of this approach.

Young adults in our previous studies expressed strong interest in both sleep and health feedback. Our current R34-funded study is testing sleep feedback alone, and our goal is to develop a program that is appealing to young adults. We will use this information to optimize and automate future intervention iterations. Inclusion of a condition in which health feedback/advice is limited to the OURAM™ mobile app. Our goal is to motivate alcohol behavior change.

Screening: We will recruit and screen subjects using methods [name] has used successfully for other studies of heavy-drinking young adults, including online ads/social media posts (e.g., Facebook, Instagram, Snapchat), and notices posted around local

colleges and the community. Interested individuals who contact investigators by phone or email or who respond to mobile ads will be directed to complete a 5-minute, web-based pre-screening survey. Before completing the pre-screener, volunteers will provide informed consent. Following completion of the pre-screener, research staff will contact potential subjects and inform them of their initial eligibility status. Those who meet initial criteria will attend an intake to provide written informed consent and complete final screening for inclusion/exclusion criteria. Eligible individuals will be randomized to their condition to begin immediately after intake.

Randomization to Condition: [name] will create the randomization list, stratified by gender and implemented through an electronic clinical trial management system to ensure allocation concealment.

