Photoplethysmography (PPG) Sensor: For 6 weeks following randomization, all subjects will wear a marketed PPG sensor, OURATM, daily. We will obtain the following health data (i.e., sleep duration, efficiency, latency, awakenings, % of time in sleep stages, bed/wake times, HRV, RHR). PPG is a non-invasive, low-cost technology that uses a light source and a photodetector at the skin surface to measure physiological parameters such as RHR, HRV, temperature, motion, movement. [61] PPG sensors are easy to use, discrete, low cost, and suitable for use in non-clinical/research settings, thereby enhancing ecological validity. PPG, including OURATM, is reliable/valid for HRV/RHR[62-65] and sleep stage prediction relative to actigraphy and PSG.[49, 50, 66-68]

At intake, the Research Coordinator will demonstrate how to wear and charge the OURATM (device needs charging every 7 days). To encourage OURATM adherence, we will provide daily reminders and support including when to recharge, and compensation for wearing and returning them, which we used successfully in our other studies. We will monitor OURATM use for all subjects through the OURATM Teams dashboard. Subjects in Assessment will not have access to the OURATM mobile app. We will sync their data to one of our study phones at the Week 6 visit. The OURATM ring can hold 6-weeks of data. Subjects in Feedback will have the OURATM mobile app downloaded on their phone to sync their data daily and receive immediate health feedback. They will then receive 3 electronic feedback reports sent via text/email at Weeks 2, 4 and 6, for which we will use the OURATM Teams dashboard.

Diary Self-Monitoring: All subjects will complete daily alcohol and sleep diaries for 6 weeks following intake, using diaries from our current R34-funded study. We will program diaries in MEI Research and send links via text message each morning. To encourage adherence, we will compensate subjects \$1 for each completed daily diary, a successful strategy in our prior research. We will monitor use via the MEI Research dashboard.

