Follow-up Visits and Exit Interviews: At Weeks 6 and 10, all subjects will complete follow-up visits remotely via ZOOM (HIPAA-compliant and password-protected) which will be recorded using ZOOM with subjects' consent. Using remote procedures to conduct follow-up visits for our current R34-funded study and prior studies has resulted in very high retention (i.e., 95%). Follow-up visits will assess alcohol use, health characteristics, and the feasibility and acceptability of self-monitoring activities and health feedback/advice. At the Week 6 follow-up, we will conduct exit interviews to evaluate helpful components. For subjects in the assessment group, we will also sync their OURATM data to the study phone at Week 6.

Randomization:

Subjects will be randomly assigned to 1 of 2 conditions: (1) Assessment (n=30) or (2) Feedback (n=30). The *Assessment* group will not have access to the OURATM mobile app and will not receive any health feedback. The *Feedback* group will have access to the OURATM app and will receive feedback. The OURATM app provides daily summaries of HRV, RHR, and sleep that subjects can view on the app. In addition, every 2 weeks, we will send a written report via text/email that: (1) summarizes subjects' alcohol use and the links with their HRV/RHR/sleep data and (2) provides health advice tailored to this data.

Intervention Conditions: Eligible subjects will be randomized to: (1) Assessment or (2) Feedback. All subjects will begin wearing an OURATM right after intake and will complete daily diary assessments.

Assessment (A) (n=30): Subjects in this group will only monitor their health/behaviors and will not receive any health feedback or advice. They will wear the OURATM daily and complete daily electronic diaries about bedtime behaviors (e.g., amount/timing of alcohol use) and their sleep for 6 weeks. Diaries will be programmed in MEI Research and sent via text message each morning, a successful procedure for our current R34-funded study. These subjects will not have access to the OURATM mobile app. We will sync their data to one of our study phones at the Week 6 visit. The OURATM ring can hold 6-weeks of data.

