4.3.3 Study Visits (is applicable)

Table 1. Schedule of Assessments

Variables	Assessments	Intake	Intake-Wk 6	6, 10
Eligibility/ Lab/ Medical	Demographics	X		
		X		
	The M.I.N.I.	X		
	AUDIT-C	X		
Alcohol/ Health Outcomes	TLFB	X		6, 10
	PROMIS™ measures	X		6, 10
	Physical fitness	X		6, 10
	BYACCQ	X		6, 10
	PSQ	X		6,10
	TPB	X		6
		X		6, 10
	DSQ	X		6,10
	Munich Chrono Type Questionnaire	X		
	ME Questionnaire	X		
	Alcohol/sleep diaries		X	
	COVID-19 Experiences Questionnaire	X		6,10
	OURA™ HRV, RHR, sleep		X	
Feasibility	OURA™ use metrics		X	
Acceptability	Treatment eval; exit interview			6

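### The Aim 2.1-2.2 mixed models name no term for gender, the randomisation stratum, so their reported standard errors may be slightly too wide

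*Combined protocol and SAP*

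**What the plan says.** In section 4.1 (Randomization to Condition) the list is "stratified by gender and implemented through an electronic clinical trial management system to ensure allocation concealment". No other factor is named, and the section does not say whether the list is blocked or otherwise balanced within gender.

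Section 4.4.3 then treats the aims differently:

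- **Aim 1:** "mixed effects models with condition and sex as between-subject factors and time as a within-subject factor", controlling for baseline drinks.
- **Secondary alcohol outcomes:** "We will also use the same modeling approach for secondary alcohol outcomes". Section 4.4.6 repeats this sentence.
- **PROMIS sleep (Aim 2.1):** "sleep quality and sleep-related impairment self-ratings, controlling for baseline, using mixed effects models".
- **Ring sleep, HRV and RHR (Aims 2.1-2.2):** "We will also analyze OURATM sleep, HRV, and RHR data (summarized over 2-week periods) using mixed effects models".

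No other section supplies a sex or gender term for the last two groups. Section 4.4.1 sets a two-sided 5% type I error. Section 4.4.2 says the trial should yield effect size estimates for secondary outcomes to plan a larger study. Section 3.1.1 calls PROMIS sleep quality the primary sleep outcome and HRV the primary health outcome.

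**The concern.** When allocation is balanced within a stratum, the design removes that stratum's contribution to the difference between arms. A model without the stratum does not know this. It leaves the between-gender variance in the residual and reports an SE larger than the true sampling variability of the estimate.

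What is at stake is calibration. The intervals for the sleep, HRV and RHR effects, which are meant to inform a later trial, would be somewhat wider than the design warrants, and the tests would reject somewhat less than 5% of the time under the null. The wording also leaves the analyst free to fit these models with or without gender, a choice better fixed before unblinded analysis.

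**Working it through.** **The plan's own figure.** Section 4.4.2 states 80% power at 30 per group for a large difference in total drinks, with no numerical effect size. It cannot be reproduced exactly. At 30 per group the detectable difference at 80% power is 0.74 SD (t-based). If large means 0.8 SD, which is an assumption, power is 86%. This concerns Aim 1; no figure is given for Aims 2.1-2.2.

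**Inputs.** From the documents: N = 60, 30 per group, two-sided 5%, three 2-week ring summaries over 6 weeks. Assumed:

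- R², the share of variance in a person's mean outcome explained by gender: 2, 5 or 10%. For PROMIS sleep this means the share beyond baseline.
- Correlation of 0.8 between 2-week summaries. It sets the SD-unit widths but cancels from the percentages.

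**Closed form, list balanced within gender.** In units of the SD of one summary, the variance of a person's three-period mean is V = (1 + 2 × 0.8)/3 = 0.867.

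- Reported SE without the stratum: sqrt(V × 2/30) = 0.240. Half-width of the 95% interval: 2.002 × 0.240 = 0.481.
- Reported SE with the stratum: sqrt(V × (1 − R²) × 2/30), a factor of sqrt(1 − R²), using t on 57 rather than 58 degrees of freedom.
- Type I error without the stratum: 2 × [1 − Φ(1.96 / sqrt(1 − R²))].

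| R² (assumed) | sqrt(1 − R²) | Fall in reported SE | Half-width with stratum | Type I error without stratum |
|---|---|---|---|---|
| 0% | 1.000 | 0.0% | 0.481 | 5.0% |
| 2% | 0.990 | 1.0% | 0.476 | 4.8% |
| 5% | 0.975 | 2.5% | 0.469 | 4.4% |
| 10% | 0.949 | 5.1% | 0.457 | 3.9% |

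**Simulation check.** 20,000 trials per cell, N = 60, complete data, gender split 50:50 and 70:30; the Monte Carlo error of a 5% rejection rate is 0.15 points.

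- *Exact balance or blocks of 4 within gender.* Type I error without the stratum is 4.8-5.0% at R² = 2%, 4.2-4.7% at 5% and 3.8-4.1% at 10%. With it, 4.7-5.3%. Adding the stratum changes the actual SD of the estimate by only 0.0-0.3%, while the mean reported SE falls 1.0%, 2.5-2.6% and 5.2-5.3%.
- *No balance within gender.* Type I error is 4.8-5.2% with or without the stratum. Here the term changes the precision of the estimate itself: at R² = 10% its actual SD falls 4.3-4.7%. At R² = 0 the half-width rises 0.9%. Break-even is near R² = 1/57 = 1.8%.

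A separate single-time-point simulation with exact balance gives type I error without and with the term of 4.4% and 5.0% at R² = 5%, and 3.8% and 4.9% at 10%. For a true effect of 0.736 SD, power goes from 80.6% to 82.0% and from 81.2% to 84.0%.

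**Time contrasts.** A gender main effect is constant within a person, so with complete data it cancels from any within-person change. The figures above therefore apply to the overall condition effect and not to condition by time.

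**The case against.** The best defence is that the Aim 2.1-2.2 paragraph is shorthand. It also names no time factor and no covariance structure, and nobody would fit repeated 2-week summaries without time. The phrase about mixed models may simply point back to the Aim 1 model, sex included. That is possible: the term is unspecified, not excluded. But the plan carries the Aim 1 approach forward in words only to the secondary alcohol outcomes, and it restates baseline control for PROMIS sleep without mentioning sex.

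Three further points stand:

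- Under balance the estimate loses almost no real precision; only its reported SE is off, in the conservative direction.
- The size rests on an R² that the documents do not give, on complete data, and on a linear model. Section 4.4.3 allows transformations and alternative methods, to which the sqrt(1 − R²) factor need not apply.
- These are secondary aims of a 60-person proof-of-concept study, and no conclusion is shown to change.

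These points limit the importance of the matter. They do not remove it, because the change is nearly free.

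A reader might also infer that the ring models are deficient because they lack baseline adjustment. The documents do not support that. Section 4.1 says "For 6 weeks following randomization, all subjects will wear a marketed PPG sensor, OURATM, daily", and Table 1 in section 4.3.3 lists "OURA™ HRV, RHR, sleep" only for intake to Week 6. No pre-randomisation ring value exists to adjust for.

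**Conclusion.** The point holds as a minor improvement. For the overall condition effect, if the list is balanced within gender, the models as written would report SEs larger than they need be: adding the stratum would cut them by about 1.0, 2.5 or 5.1% at an assumed gender R² of 2, 5 or 10%. Type I error would be about 4.4% at R² = 5% and 3.9% at 10%, instead of the nominal 5%. If the list is not balanced within gender, type I error is nominal either way and the term helps only above an R² of about 1.8%.

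A reader might go further and infer biased condition effects or inflated false positives. Neither follows: randomisation protects the estimate, and the error rate is at or below nominal. Nor do the documents support a large gain. An R² of 20-30% would narrow intervals by about 11-16%, since sqrt(0.8) = 0.894 and sqrt(0.7) = 0.837, but nothing in the plan points to values that high.

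**What to change.** Before unblinded analysis, add one sentence to section 4.4.3: the Aim 2.1-2.2 mixed models include the gender stratum used for randomisation as a between-subject factor, as the Aim 1 model does with sex. Name the variable as it was used in the randomisation list, since section 4.1 says gender and section 4.4.3 says sex.

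The change is to wording only. Gender is already needed for the list and is summarised under section 4.4.4, so no new data are collected. With two gender levels the statistical cost is one degree of freedom. If gender turns out not to be prognostic, the interval widens by under 0.1% with a balanced list and by about 0.9% without balance.

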4.4.4 Analysis of Subject Characteristics (if applicable)

We will use descriptive statistics were used to summarize frequencies and percentages of sociodemographic characteristics (age, race, ethnicity, gender, college status) and clinical characteristics (drinking, sleep, and other health behaviors).

4.4.5 Interim Analysis (if applicable)

N/A

4.4.6 Handling of Missing Data

We will also use the same modeling approach for secondary alcohol outcomes: drinks per drinking day, % heavy drinking, abstinent days (summarized in 4-week periods), and alcohol-related consequences, controlling for baseline, and will focus on effect size estimation rather than statistical testing. Using all repeated measures on individuals in the context of a mixed model will allow us to assess temporal patterns of change over time and to use all available data on individuals. Thus, this approach helps to avoid imputation of missing data and allows us to obtain unbiased and efficient estimates of the main and interactive effects. Mixed models will account for the correlation in alcohol outcomes measured in the same individual. We will use the Schwartz-Bayesian Information Criterion to elect the best-fitting variance-covariance structure. We will consider time as a categorical

factor but will also test whether alcohol outcomes change linearly by condition over time. If an alcohol outcome is not normally distributed, we have several options including transforming data, utilizing alternative methods (e.g., generalized linear mixed models, nonparametric tests, Poisson and negative binomial generalized linear mixed models for count data).

5 Trial Administration

5.1 Ethical Considerations: Informed Consent/Accent and HIPAA Authorization

Consent forms will be Institutional Review Board (IRB)-approved and the participant will be

This section should include any applicable ethical considerations. They should also be addressed in the Informed Consent form, including if informed consent and/or HIPAA authorization will be obtained or a waiver of informed consent and/or HIPAA authorization will be requested. The Informed Consent form should be included as an attachment to the protocol.

Describe the following:

- Any possible deception
- Rationale if payment will be provided for participation.
- Any sensitive data that may be collected and how it will be protected.
- Any possibility that a previously unknown condition (disease, genetic disposition, etc.) will be discovered as the result of the study procedures and how this will be handled.
- Any information that may be added to the subject's permanent medical records with rationale.
- If informed consent/assent and HIPAA authorization will be obtained, the following should be addressed:
 - Who will obtain consent/authorization
 - When and where will the consent/authorization discussion occur
 - How will subject privacy be assured
 - How will consent/authorization be documented
 - How will subject understanding of the study be assessed
 - What steps are in place to avoid subject coercion

If your study involves children, additional information should be provided to describe:

- How parental permission will be obtained
- From how many parents will parental permission be obtained
- Whether permission will be obtained from individuals other than parents, and if so, who will be allowed to provide permission. The process used to determine these individual's authority to consent for the child should be provided
- Whether or not assent will be obtained from the child
- How will assent be documented
- Whether child subjects may be expected to attain legal age to consent to the procedures for research prior to the completion of their participation in the research. If so, describe the process that will be used to obtain their legal consent to continue participation in the study. Indicate what will occur if consent is not obtained from the now-adult subjects.

asked to read and review the document. The members of the research team will explain the research study to the participant and answer any questions that may arise. This conversation will take place in a private room.

Participants will have the opportunity to carefully review the written consent form and ask questions prior to signing. The participants should have the opportunity to discuss the study with their family or surrogates or think about it prior to agreeing to participate. The participant will sign the informed consent document prior to any procedures being done specifically for the study. Participants must be informed that participation is voluntary and that they may withdraw from the study at any time, without prejudice. A copy of the informed consent document will be given to the participants for their records

We will not be enrolling participants with limited decision-making capacity. We plan to exclude individuals with current serious psychiatric or medical illnesses. The research assistant will read and review the consent form either in-person or via televideo while COVID-19 social distancing requirements remain in place. Due to the ongoing COVID-19

pandemic, it is not always possible to consent a new study participant in person. Due to this, many participants will be consented via televideo, therefore a physical consent form will not be signed by the participant. Instead, a REDCap consent will be created, where participants will be able to view the entire consent form and then electronically sign/date/initial the consent form. The research assistant will share their screen while on televideo so the consent form can be read along with the participant. This is to explain the study in detail to the participant, so they are aware of all aspects of the study and fully informed. Participants will be able to ask research staff any questions during this consenting period. The research assistant will then ask the potential participant various questions about the consent form and study protocol to ensure the prospective participant sufficiently understands the study and the nature of their consent to participate. If concerns arise that a potential individual does not have sufficient capacity to provide informed consent, we will have a clinical member of the team conduct a mini mental status exam to verify capacity. We will allow sufficient time for research staff to explain the study and potential participants to review the consent, study procedures, and ask questions to avoid coercion.

The data will be stored in a locked room for 7 years after the final data is collected. After this point, the Data Manager and Principal Investigator, [name], will oversee the process in which data is destroyed or de-identified.

We have obtained a Certificate of Confidentiality (CoC) issued by the NIH. Once granted, the researchers can use this Certificate to legally refuse to disclose information that may identify the participant in any federal, state, or local civil, criminal, administrative, legislative, or other proceedings, for example, if there is a court subpoena. The researchers will use the Certificate to resist any demands for information that would identify the participant, except as explained below.

The protection offered by the CoC does not stop the research team from voluntarily reporting information about suspected or known sexual, physical, or other abuse of a child or older person, or a participant's threats of violence to self or others. If any member of the research team is given such information, he or she will make a report to the appropriate authorities. When the CoC is obtained, we will inform all active study participants.

The anticipated funding for this study is from an NIH grant (R21AA028886).

Even when a CoC is in place, the participant and their family members must still continue to actively protect their own privacy. If they voluntarily give their written consent for anyone to receive information about their participation in the research, then we may not use the CoC to withhold this information.

Participants will be paid \$30 for completing the intake, \$45 for completing the week 6 follow-up visit, and \$60 for completing the week 10 follow-up visit, total=\$135.

Participants will also be compensated for at-home monitoring activities: (1) \$1 per day for wearing the OURa (42 possible days for a total of \$42), (2) \$50 for returning the OURa, and (3) \$1 per day for completing each daily diary (42 possible days for a total of \$42). The total possible compensation for at-home monitoring is \$94. Therefore, the total possible compensation for participants is \$279. Participants will be registered through Oncore to receive payments for taking part in the study. We will use a Bank of America pre- paid debit card to provide payment. We will have to share participant name, address, and telephone number with Bank of America for ePayments and this information is communicated in the consent form. The participant will receive a card in the mail with the first payment. Each additional payment will be automatically added to the card.

